Lying within the conservative-surgical treatment spectrum for plantar fasciitis is local corticosteroid injection (CSI) therapy (15), a *minimally invasive intervention* that is relatively quick and easy for the clinician to perform in the *outpatient clinical setting*. A targeted plantar fascia injection typically combines both corticosteroid (CSI) and a local anesthetic (LA) as the substance infused (i.e. *injectate*). Administration of a CSI near the irritated plantar fascia has documented evidence of providing pain relief for up to 1 month only (16). A randomized trial performed as far back as 1956 showed *no statistical difference* between CSI and placebo (i.e., saline) with 6-18 months of follow-up recorded (17). Yet, to this day, a CSI is essentially the only immediate intervention that can be proffered in the outpatient clinic by providers that third-party payers (at least in the United States) will compensate for. In point of fact, 73% of surveyed orthopaedic surgeons *preferred CSI* to treat heel pain (18), *yet* its own preeminent foot association, the American Orthopaedic Foot and Ankle Society (14), advocates for its *judicious* use for fear of deleterious side effects, including fat pad atrophy (20) and possible rupture (21). The ambiguity surrounding corticosteroid *injection* as therapy is further substantiated from histopathologic studies involving plantar fasciitis (22-24), which *failed to demonstrate any inflammatory process*, calling into question the rationale on the use of corticosteroids altogether, which are used primarily for their potent anti-inflammatory effects (18). Reasonably, the terminology plantar *fasciitis* is perhaps a misnomer given the *degenerative* (rather than inflammatory) findings uncovered (24), which some investigators refer to as plantar *fasciosis* or plantar *fasciopathy*, given the similar tissue pathology seen in other musculoskeletal tendon disorders, or *tendinopathies* (25-28, 31).

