
Sample Size

We estimate the sample size required to answer the research question to be 50 participants.

Interventions and Interactions

Once both informed consent and enrollment have been verified, initial evaluation by the PI will be conducted on participants, and baseline assessments will be performed. The assessments include:

- Documentation of participant age at enrollment along with information on sex/gender, race, and ethnicity to ensure the study involves Inclusion of Individuals across the Lifespan
- History and physical exam
- Calculated BMI
- Documentation of referral patterns (PCP, self, or other referral)
 - If from PCP or other, documentation of what information/work-up was provided (e.g. told they have “heel spur”, given NSAIDs, exercises, etc.)
- Clinical confirmation/diagnosis of plantar fasciitis (pain at medial calcaneal tubercle)
- Dolorimeter readings of PPT # (pressure algometer)
- Documentation of subjective reporting of first-step pain (yes/no)
- Foot posture score
- Heel tenderness score
- Initial X-ray (notation and measurement of heel spur) of the symptomatic foot/heel will be performed, if not already completed
- Initial diagnostic musculoskeletal US (PF thickness and echogenicity; fat pad thickness)
- Patient completed baseline self-assessment of both “general heel pain” and “first step pain” (VAS PROM)
- Patient completed baseline self-assessment of foot function (FFI PROM)

At this point, the patient will be block allocated to their study arm, having been randomized in a double-blind fashion by the clinical coordinator. This individual will facilitate safe record-keeping and the processes required to maintain the double-blind design of this study. We will specifically conduct the study in a permuted block design to ensure a 1:1 ratio for the two treatment intervention groups. The study arms are as follows:

- Group 1 - CSI/LA injection
- Group 2 - LA/Saline injection

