A nurse or staff member will open a previously prepared and sealed opaque envelope (prepared beforehand by the clinical coordinator) labeled with the participant ID of the patient, which will be unique to the individual and different from their MRN. In this envelope, they will discover the patient's assigned treatment arm. The nurse or staff member will then prepare the syringe with the assigned treatment arm. Once the syringe is filled with the designated substance, the syringe will be wrapped with opaque tape or dark Coban wrap to conceal the contents in the

syringe for both the PI and study participant. The participant's skin will be steriley prepped with alcohol.

The PI will then administer the injection using an infracalcaneal needle peppering technique as follows:

1. The hypodermic needle is inserted using infracalcaneal injection approach.
2. The hypodermic needle is withdrawn while at the same depositing injectate.
3. The hypodermic needle is redirected without emerging from the skin.

The PI will perform steps 1-3 standardly 20-25 times. Following the completion of the injection and clinical observation, the patient will receive home care and follow-up instructions which will include the standardized teaching of 3 exercises (calf stretching, plantar fascia specific stretching, and plantar fascia loading exercise). Patients will be sent home with an exercise diary to record when and if they complete the instructed exercises with directions to bring the diary to the next visit. Patients will receive 1 phone call between this visit and the next to check in on their exercise progress and remind them to complete the exercise diary.

The patient will be seen at follow-up visit #1 for evaluation and management 2 weeks post-treatment intervention. At this visit, the following assessments will be completed:

- History and physical exam
- Patient self-assessment of both "general heel pain" and "first step pain" (VAS PROM)
- Patient self-assessment of foot function (FFI PROM)
- Dolorimeter readings of PPT # (pressure algometer)
- Heel tenderness score
- Review of the exercise diary

A new exercise diary will be given to the patient. The recommended exercises will be instructed again. Patients will be encouraged to bring the diary to their next visit. To increase compliance, patients will receive 1 phone call to check in on their exercise progress and remind them to complete the exercise diary.

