The patient will return for follow-up visit #2 for evaluation and management 4 weeks post-treatment intervention. At this visit, the following assessments will be completed:

- History and physical exam
- Patient self-assessment of both "general heel pain" and "first step pain" (VAS PROM)
- Patient self-assessment of foot function (FFI PROM)
- Dolorimeter readings of PPT # (pressure algometer)
- Heel tenderness score
- Review of the exercise diary

A new exercise diary will be given to the patient. The recommended exercises will be instructed again. Patients will be encouraged to bring the diary to their next visit. The patient will be called 1 time to remind them to complete their exercise diary between visits.

The patient will return for follow-up visit #3 for evaluation and management 8 weeks post-treatment intervention. At this visit, the following assessments will be completed:

- History and physical exam
- Patient self-assessment of both "general heel pain" and "first step pain" (VAS PROM)
- Patient self-assessment of foot function (FFI PROM)
- Dolorimeter readings of PPT # (pressure algometer)
- Heel tenderness score

- Review of the exercise diary

A new exercise diary will be given to the patient. The recommended exercises will be instructed again. Patients will be encouraged to bring the diary to their next visit. The patient will be called 1 last time to remind them of their exercise diary and encourage them to complete it.

The follow-up visit #4 will be the final study visit. This visit will occur 12 weeks post-treatment intervention. At this visit, the following assessments will be completed:

- History and physical exam
- Patient self-assessment of both “general heel pain” and “first step pain” (VAS PROM)
- Patient self-assessment of foot function (FFI PROM)
- Dolorimeter readings of PPT # (pressure algometer)
- Heel tenderness score
- Review of the exercise diary
- Final diagnostic musculoskeletal US (PF thickness and echogenicity; fat pad thickness)
- Exit survey

Evaluation Schedule Summary

Procedures	Screening -42 to -1 days	Injection day 0	Week 2 +/- 3 days	Week 4 +/- 3 days	Week 8 +/- 3 days	Week 12 +/- 3 days
Review Study Procedures, Informed Consent, and Privacy Authorization	x	x				
Eligibility Criteria for Study Entry	x	x				
Patient Demographics	x					
Patient Medical/Surgical History	x	x				
Height, Weight, and Vital Signs	x	x	x	x	x	x
Foot & Ankle Physical Exam	x	x	x	x	x	x

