Presentation of Exercise Therapy (targeted stretching and strengthening)	x	x	x	x	x	x
Clinical Observation	x					
X-ray of Affected Foot	x					
Ultrasound of Affected Foot	x					x
Randomization		x				
Study Therapeutic Treatment Intervention (infracalcaneal needle peppering injections)		x				
Evaluation of Injection Site		x	x	x	x	x

Subject Self-Assessments - VAS PROM (for both general heel pain and first step pain) - FFI PROM	x	x	x	x	x	x
Exercise Diary & Instruction of the 3 Exercises		x	x	x	x	x
Foot Posture	x	x				
Heel Pressure Threshold using Dolorimeter	x	x	x	x	x	x
Heel Tenderness Score	x	x	x	x	x	x
Exit Survey						x

*Not on schedule: reminder phone call between study visits to encourage exercise diary completion and compliance.

Outcome Measure(s)

Patient Assessments

- Heel Tenderness VAS PROM
- First Step Pain VAS PROM
- FFI PROM
- Exercise Diary
- Exit Survey at completion of study

Physician Assessments

- Baseline and subsequent foot and ankle physical exam, heel pressure threshold, and heel tenderness score
- X-ray and ultrasound imaging
 - Our research team will be the first to examine musculoskeletal ultrasound imaging obtained both before and after an infracalcaneal peppering injection in participants with chronic plantar fasciitis. Musculoskeletal ultrasound has become more established in the medical literature as a reliable objective measure of plantar fasciitis, with thickness measurements >4.0mm correlating with clinical symptoms (40). Musculoskeletal ultrasound's utility here would enable our investigators to assess for any quantifiable tissue changes associated with our intervention.

Patient Retention

Every effort will be made to retain patients in the study to ensure complete data collection. During the study consent process, potential study participants will be educated regarding the importance of full participation in all visits. Patients will be reminded of their upcoming appointment via phone call or email. Patients will also be reminded about their follow-up visits at all clinic visits.

Patient/study participant compensation will occur at certain study visits. Study participants will receive a paid total of \$100.00 if all scheduled study visits are completed.

Study Visit #1 – injection day	\$20.00
Study Visit #2 – 2 weeks post-treatment intervention	No payment. Next payment at 4-week follow-up study visit (visit #3).
Study Visit #3 – 4 weeks post-treatment intervention	\$40.00

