Study Visit #4 – 8 weeks post-treatment intervention	No payment. Next payment at 12-week follow-up study visit (visit #5).
Study Visit #5 – 12 weeks post-treatment intervention	\$40.00

Analytical Plan

Results will be analyzed initially using descriptive statistics. Comparison between groups will be done using chi square tests for proportions, and t-tests or ANOVA procedures for continuous variables. Regression analysis will be performed to identify independent outcome predictors. Other inferential statistical analysis will be conducted as appropriate.

Human Subjects Protection

All patients ages 18 years and up with a diagnosis of plantar heel pain will be screened for inclusion into the study. The study will be conducted in accordance with the current IRB-approved clinical protocol; ICH GCP Guidelines adopted by the FDA; relevant policies, requirements, and regulations of the clinical test site IRB; and applicable federal agencies.

Patients who meet the inclusion criteria will be asked to participate in the research study and provided ample time and encouragement to ask questions and discuss the study with others (medical providers, family, friends, etc.). A copy of the informed consent form will be provided to the patient. The study team will answer all questions.

Subjects may withdraw from the study at any time for any reason at their request. Otherwise, participants will be followed as per the protocol. Attempts will be made to collect clinical data from withdrawn subjects. There will be no replacement of subjects who withdraw from the study.

Subject Recruitment Methods

The study will recruit patients who present to the Atrium Health Wake Forest Baptist Department of Orthopaedic Surgery-Podiatry Services practice located in High Point, North Carolina with symptoms of plantar heel pain. In order to approach patients that have received care at this practice in the past, we will create an i2b2 query to result a list of patients seen by [name] and diagnosed with plantar fasciitis within the last 3 years (11/1/2020 – 11/1/2023). These patients will be contacted by the study coordinator to introduce the study, gauge their interest, and begin the pre-screening process if they opt in to doing so.

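### Fat pad thickness: the arm comparison states no baseline term, and an ANCOVA on the scan already taken would be modestly more precise

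*Combined protocol and SAP*

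**What the plan says.** The Analytical Plan is one short paragraph. Its method for comparing arms is "Comparison between groups will be done using chi square tests for proportions, and t-tests or ANOVA procedures for continuous variables". It then adds "Regression analysis will be performed to identify independent outcome predictors" and an open clause allowing other inferential analyses. It mentions no covariate, change score or repeated-measures model.

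The background reports that a professional foot society advises judicious steroid use for "fear of deleterious side effects, including fat pad atrophy (20) and possible rupture (21").

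Under Interventions and Interactions, the assessments before allocation include "Initial diagnostic musculoskeletal US (PF thickness and echogenicity; fat pad thickness"), and the week-12 visit includes "Final diagnostic musculoskeletal US (PF thickness and echogenicity; fat pad thickness"). The Evaluation Schedule Summary agrees: ultrasound at screening and at week 12 only.

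Under Outcome Measure(s), the protocol says "Our research team will be the first to examine musculoskeletal ultrasound imaging obtained both before and after an infracalcaneal peppering injection", and that the aim is to "assess for any quantifiable tissue changes associated with our intervention".

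The needle technique is common to both arms: "The PI will then administer the injection using an infracalcaneal needle peppering technique as follows". The arms differ in the injectate, steroid with local anaesthetic against local anaesthetic with saline.

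**The concern.** The protocol questions continued steroid use partly on grounds of harm, and fat pad thickness is an objective measure bearing on one harm that it names. Because both arms are peppered, a before-to-after change within an arm mixes any needle effect with any steroid effect. Only the randomised contrast between arms isolates the steroid.

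For that contrast, the stated method leaves open whether week-12 values or changes are compared, and does not require the baseline scan to be used. Which of the two is more precise depends on the correlation between scans: week-12 values below 0.5, changes above it. That correlation is not given. ANCOVA removes the need to choose and is close to the best of the three at any plausible correlation. At stake is the width of the interval that the pilot can offer a later trial.

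**Working it through.** **Inputs from the documents.** Total sample size 50 (Sample Size) and 1:1 permuted-block allocation (Interventions and Interactions), hence n = 25 per arm. The figure of 50 comes without alpha, power, effect size or SD, so it cannot be reproduced and serves here only as an input.

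**Assumptions.** All 50 are scanned at week 12; two-sided 95% intervals; thickness in SD units, with the same SD at both times and in both arms; correlation r between the two scans of 0.3, 0.5, 0.8 or 0.9.

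**Variance of the estimated arm difference.**

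- Week-12 values: 2/n
- Change scores: 2(1 − r) × 2/n
- ANCOVA: (1 − r²) × (2/n) × [1 + 1/(2n − 4)]; the bracket is the cost of estimating the baseline slope

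The half-width is the 97.5% t quantile times the square root of the variance, on 2n − 2 degrees of freedom for the first two and 2n − 3 for ANCOVA.

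**Worked case, n = 25, r = 0.8.** 2/n = 0.08.

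- Week-12 values: SE = √0.08 = 0.283; half-width 0.569
- Change: SE = √(0.4 × 0.08) = 0.179; half-width 0.360
- ANCOVA: SE = √(0.36 × 0.08 × (1 + 1/46)) = 0.172; half-width 0.345

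**All cases, 25 per arm (half-widths in SD).**

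| r | Week-12 values | Change | ANCOVA | ANCOVA narrower than change | ANCOVA narrower than week-12 |
|---|---|---|---|---|---|
| 0.3 | 0.569 | 0.673 | 0.549 | 18% | 4% |
| 0.5 | 0.569 | 0.569 | 0.498 | 12% | 12% |
| 0.8 | 0.569 | 0.360 | 0.345 | 4% | 39% |
| 0.9 | 0.569 | 0.254 | 0.251 | 1% | 56% |

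Simulation (10,000 trials per case) gave ANCOVA standard errors of 0.248, 0.172 and 0.124 at r = 0.5, 0.8 and 0.9, in agreement with the formula.

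**Where the gain stops.** ANCOVA beats week-12 values once r exceeds about 0.15. Leaving aside the slope cost, its variance relative to change is (1 + r)/2, so the advantage fades as r rises. With the slope cost, the variances are equal at r = 2/(1 + 1/46) − 1 = 0.957. At r = 0.95 both half-widths are 0.180.

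**Fewer scans.** If 75% were scanned (0.75 × 25 = 18.75, about 19 per arm), the half-widths at r = 0.8 are 0.658, 0.416 and 0.401. At r = 0.95, change is marginally better (0.208 against 0.209). The 75% is borrowed: the protocol gives it as a capture target for the patient-reported outcomes, not for ultrasound.

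**If atrophy is confined to a minority.** Take r = 0.8, so the SD of change is √0.4 = 0.632, and let 10% of the steroid arm lose 2 SD of change, or 20% lose 3 SD. The mean shift is 0.1 × 2 × 0.632 = 0.13 SD, or 0.2 × 3 × 0.632 = 0.38 SD. Mean simulated half-widths (50,000 trials per case) for week-12 values, change and ANCOVA are 0.586, 0.388 and 0.376, or 0.642, 0.469 and 0.460. Power is 7%, 9% and 10% in the first pattern, and 20%, 33% and 34% in the second.

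**The case against.** The strongest reply is that nothing here is wrong. The scans are explicitly meant to show tissue change, so change scores are the natural reading, and against those the gain at high correlation is a few per cent. ANOVA can include a repeated-measures form, whose group-by-time test with two scans is the change-score test. A regression for predictors that contained arm and baseline scan would itself be ANCOVA. The open clause excludes nothing.

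The outcome is also peripheral. The Objectives concern feasibility and two patient-reported outcomes. Fat pad thickness is one ultrasound item, never named as an endpoint or safety outcome, and the stated rationale for ultrasound speaks of plantar fasciitis and not of the fat pad. The link to harm comes from reading the background together with the visit list. Every magnitude above is assumed, and if only a minority is affected no method has much power.

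Most of this stands. It limits the point to efficiency and keeps it minor. What it does not answer is that permission is not specification: the regression sentence concerns predictors, not the arm difference, and week-12 values are as permissible under the text as changes. Stating the model beforehand also prevents the choice being made once the scans have been seen.

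**Conclusion.** The point holds as a minor gain in efficiency and pre-specification. Against change scores, the reading that the protocol's own description suggests, ANCOVA's interval is about 4% narrower at a correlation of 0.8, 12% to 18% narrower at 0.5 to 0.3, and no narrower from about 0.95. The larger gains, 39% and 56% at 0.8 and 0.9, apply only if week-12 values alone were compared. These figures rest on 25 scanned per arm, equal SDs and the assumed correlations.

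A reader might infer three stronger things. One is that a week-12-only test is planned; the documents do not say so, and the intention to examine images from before and after points the other way. A second is that the stated test is invalid or biased; under randomisation it is neither. A third is that a non-significant difference would be read as absence of atrophy; no such interpretation is stated.

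**What to change.** Add to the Analytical Plan:

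> The arm difference in week-12 fat pad thickness will be estimated by ANCOVA with the baseline scan as covariate and reported with its 95% CI; individual changes will be plotted by arm.

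Present the result as an estimate, not as a test. The plot is there to show loss confined to a few patients, which a mean difference would show poorly.

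The cost is one sentence and one plot, with no new scans, visits or patients. Statistically it is one degree of freedom and the slope-estimation factor of 1 + 1/46, about 2% in variance at 25 per arm. The change does not make the interval narrow at this sample size.

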Successful completion of our proposed pilot study addresses a critical knowledge gap in the treatment of chronic plantar fasciitis and breaches the translational roadblock of clinical implementation. The results from this rigorous pilot study will provide the framework for our anticipated full-scale efficacy trial with the potential of affording the clinician an upgraded evidenced-based treatment option that has been demonstrated to be safe, effective, and reproducible.

Objectives

1. Assess feasibility of infracalcaneal peppering injection technique with and without CSI in the management of patients with chronic plantar fasciitis.
 - a. Feasibility of recruitment, randomization, retention, patient and physician time constraints, and tolerability of treatment will be assessed. Clear quantitative benchmarks and a number needed to treat will be achieved for planned utilization in a subsequent full-scale efficacy trial.
2. Assess the efficacy of infracalcaneal peppering injection with and without CSI for reduction in pain utilizing two validated patient reported outcomes measures (PROMs): the Visual Analog Scale (VAS) and Foot Function Index (FFI), administered at baseline, then at 2, 4, 8, and 12 weeks. Minimal Important Difference (MID) calculations for both VAS and FFI PROMs, specifically for plantar fasciitis, have already been investigated/established and will be used as a reference.
 - a. Greater than 75% of these PROMs from ALL cumulative target dates will be captured, providing a target number needed to treat (NNT) to conduct a full-scale efficacy trial investigation.

Methods and Measures

Design: A randomized, double-blind placebo-controlled pilot study at one single institution

Setting: Atrium Health Wake Forest Baptist Department of Orthopaedic Surgery-Podiatry Services practice located in High Point, North Carolina

Subject Selection Criteria

Inclusion Criteria

- Men and women 18 years of age and older
- Patient reported history of plantar heel pain *and* confirmed clinical tenderness of pain with direct palpation of the medial calcaneal tubercle on baseline exam
- Diagnosis of chronic plantar fasciitis, defined for study purposes as symptoms greater than or equal to 6 weeks in duration

Exclusion Criteria

- Individuals less than 18 years of age
- Pregnancy

- History of receiving a local heel injection (i.e. CSI or other injectate) within the last 3 months
- Prior heel trauma or surgery
- Allergy to local corticosteroid or local anesthesia

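### The plan collects a baseline and four follow-ups of each continuous outcome but does not commit to baseline adjustment or to a model for the repeated visits

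*Combined protocol and SAP*

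**What the plan says.** The Analytical Plan is four sentences long. After descriptive statistics, it assigns chi-square tests to proportions and "t-tests or ANOVA procedures for continuous variables". Two broader sentences follow: "Regression analysis will be performed to identify independent outcome predictors" and "Other inferential statistical analysis will be conducted as appropriate".

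Objective 2 is to assess efficacy on VAS and FFI, "administered at baseline, then at 2, 4, 8, and 12 weeks". Interventions and Interactions and the Evaluation Schedule Summary add pressure threshold at the same times. The schedule also marks all three measures at both screening (up to 42 days before injection) and day 0.

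The Sample Size section is one sentence: "We estimate the sample size required to answer the research question to be 50 participants". Allocation is 1:1, so about 25 per arm. No section mentions a baseline covariate, ANCOVA, change scores, a mixed model, or the visit at which the arms are compared.

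**The concern.** A t-test or one-way ANOVA on follow-up scores ignores the baseline, and a t-test on change scores uses it with a fixed weight of one. ANCOVA estimates the weight from the data. In a randomised trial all three are unbiased for the arm difference, so what is at stake is interval width, which matters with about 25 patients per arm.

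There is also a prespecification problem. With score type, adjustment and visit all open, the choice can be made after the results are seen. The regression sentence does not close the gap, because its stated purpose is to find predictors and it lists no covariates. The catch-all sentence permits adjustment without committing to it.

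A further problem arises only if the ANOVA wording is meant to cover standard repeated-measures ANOVA. That method drops anyone who misses a single visit.

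**Working it through.** **Inputs.** From the documents: N = 50, 1:1 allocation, one pre-injection value and four follow-ups. Assumed, because the documents are silent: equal SDs in the arms and over time, two-sided 95% intervals, and a baseline-to-follow-up correlation ρ of 0.2 to 0.7. The plan's figure of 50 comes with no alpha, power, effect size or SD, so it can be neither reproduced nor refuted.

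**Variance of the arm difference**, relative to a post-score t-test (set to 1):
- change score: 2(1 − ρ)
- ANCOVA: (1 − ρ²) × [1 + 1/(N − 4)]. The bracket is the cost of estimating the covariate slope; at N = 50 it is 1 + 1/46 = 1.0217.

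**Equivalent sample size** for ANCOVA on 50 patients:
- against post score: 50 / [(1 − ρ²) × 1.0217]; at ρ = 0.5 this is 50 / (0.75 × 1.0217) = 65.2
- against change score: 100 / [(1 + ρ) × 1.0217]; at ρ = 0.3 this is 100 / (1.3 × 1.0217) = 75.3

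**95% CI half-width**, in SD units, one visit, complete data on 25 per arm:
- post score: t(48) × √(4/50) = 2.0106 × 0.2828 = 0.569
- change score: 0.569 × √[2(1 − ρ)]
- ANCOVA: t(47) × √[(4/50) × (1 − ρ²) × 1.0217]

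| ρ | Equivalent N, post score | Equivalent N, change score | Half-width, post | Half-width, change | Half-width, ANCOVA |
|---|---|---|---|---|---|
| 0.2 | 51.0 | 81.6 | 0.569 | 0.719 | 0.564 |
| 0.3 | 53.8 | 75.3 | 0.569 | 0.673 | 0.549 |
| 0.5 | 65.2 | 65.2 | 0.569 | 0.569 | 0.498 |
| 0.7 | 96.0 | 57.6 | 0.569 | 0.441 | 0.411 |

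Simulation of 40,000 trials at each correlation gave 51.0, 53.8, 65.0 and 96.3 against post scores, and 81.6, 75.4, 66.2 and 57.6 against change scores.

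**Break-even with post scores.** Setting the ANCOVA variance to 1 gives ρ = √(1 − 1/1.0217) = 0.146, or about 0.15 when judged by half-width. At ρ = 0.1, 50 patients under ANCOVA match about 49 under the post-score test, a slight loss.

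**Fewer patients at the visit.** The smallest count above 75% of 50 is 38, taken as 19 per arm, with penalty 1 + 1/34. Half-widths at ρ = 0.2, 0.3, 0.5 and 0.7:
- post score: 0.658 throughout
- change score: 0.832, 0.779, 0.658, 0.510
- ANCOVA: 0.655, 0.637, 0.579, 0.477

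**Repeated-measures ANOVA reading only.** Objective 2a sets the capture target: "Greater than 75% of these PROMs from ALL cumulative target dates will be captured". If 75% of the four follow-up forms are captured, complete cases are about 37 of 50 when the same people miss every visit (0.75 × 50 = 37.5). They are about 16 when misses are independent (0.75⁴ × 50 = 15.8). At 90% capture the two figures are 45 and about 33 (0.9⁴ × 50 = 32.8). These are illustrations, not forecasts.

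**The case against.** The strongest reply is that little depends on this. The study is a pilot with feasibility first, and its stated products are benchmarks and a number needed to treat (Objective 1a: "Clear quantitative benchmarks and a number needed to treat will be achieved for planned utilization in a subsequent full-scale efficacy trial"). That number rests on proportions, which ANCOVA on a continuous score does not directly sharpen. No margin, power target or decision rule is attached to a continuous arm difference. This stands, and it keeps the point modest. It does not remove it, because Objective 2 still calls for an efficacy assessment on VAS and FFI.

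A second reply is that the gain rests on a correlation nobody has stated. Against post scores it is about 1% of half-width at 0.2 and 3.5% at 0.3, and becomes material only around 0.5 (12%). This is also fair, and is why a range is shown. Where the correlation is low, however, ANCOVA's advantage over change scores is at its largest, and the plan does not say which score would be used.

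Third, with two arms a one-way ANOVA adds nothing to a t-test, so the authors may have meant covariate or repeated-measures forms. If so, the plan should say it; as written, the text commits to neither. Finally, 75% is a minimum target and the protocol describes retention measures, so the complete-case counts show only how sensitive that one reading is.

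**Conclusion.** The concern holds. The plan prespecifies no baseline adjustment, score type, comparison visit or longitudinal model for outcomes measured before injection and four times afterwards. If the unadjusted test is run, the loss is one of precision, not validity. With 25 per arm, complete data and equal SDs, the ANCOVA half-width is 0.564 to 0.411 SD for correlations of 0.2 to 0.7. The post-score test gives 0.569 SD, and the change-score test 0.719 to 0.441 SD. The gain over post scores vanishes near a correlation of 0.15. The size of the gain depends on that unstated correlation; the gap in prespecification does not. The change should be made, but it does not threaten the feasibility objective.

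**What to change.** In the Analytical Plan, for VAS (general heel pain and first-step pain), FFI and pressure threshold, replace the t-test or ANOVA wording with: ANCOVA at a named visit, with arm as factor and the pre-injection day-0 value as covariate, reporting the arm difference with its 95% CI. The investigators must name the visit. They must also state which baseline is used, since the schedule has readings at both screening and day 0; the mean of the two is an acceptable alternative if fixed in advance.

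Single-visit ANCOVA still omits anyone without that visit. The alternative is a mixed model for repeated measures with arm, visit, arm-by-visit interaction and baseline. It keeps every randomised participant with at least one follow-up and is valid under missing at random. If it is chosen, the covariance structure and a small-sample degrees-of-freedom method should be stated too, given about 25 per arm. One of the two should be designated now as the main analysis.

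The cost is a wording change, slightly more programming and one degree of freedom for the covariate. It needs no new data, visits or patient burden.
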